All eligible participants will be scheduled for assessments at two time points: pre (baseline) and post intervention (12-weeks). The assessments consist of a battery of 8-10 questionnaires taking about 20-30 minutes to complete. Next, physiological measurements will be conducted by a trained research assistant and will take about 10 minutes to complete. Participants will receive \$30 for completing each assessments. Completed questionnaires will be coded with a study ID to protect confidentiality. All personal health information will be entered into a password protected secure server environment within UCSD-HSRC. After the baseline assessment, participants will be randomized to either the Hatha Yoga Intervention or to the Restorative Yoga Intervention. Randomization will occur through a web portal linked to a secure file providing block randomized digits that was prepared by the study statistician. There will be one block file for each site, with 30 digits in each file, allowing each site to have a balanced randomization. Research staff will not have access to the randomization file. Participants will be told of their group assignment and will be allowed to ask additional questions at that time.

Assessment Questionnaires and Measurements:

Screening: Medical record information will be used by screening physicians to complete the Back Pain History Questionnaire which will allow the investigators to assign a descriptive diagnosis based on the Quebec Nomenclature on Activity Related Spinal Disorders¹⁰⁴. The measure has been used in previous VA studies¹⁰⁵⁻¹⁰⁷. Additional information on co-morbid diagnoses, opioid pain medication usage, and ongoing treatments will also be collected including information on TBI, PTSD and other psychological diagnoses, and substance use.

Demographics: A brief questionnaire will assess age, gender, education, race/ethnicity, employment status, military rank and duties, and combat status.

Pain interference with daily function and pain severity will be measured with the short version of the Brief Pain Inventory (BPI).¹⁰⁸ Pain interference will serve as the primary outcome. The BPI has been validated with CLBP.¹⁰⁹ The pain interference score is the mean of the 7 interference items. The pain severity score is the mean of 4 severity items. The BPI has good reliability (alpha 0.77 - 0.91).

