Physical Measures. The integrity of physiological measure will be maintained by having multiple research staff trained by local UCSD experts in the use of the inclinometer, dynamometer, heart monitors, and core strength tests. Following initial training, research staff will conduct a series of 6 mock measurements to ensure reliability of measurement. Any problems will be tracked and addressed with re-training.

Spinal Range of Motion (ROM) will be measured using a digital inclinometer, which isolates lumbar

ROM (flexion and extension). The device uses a precise optical angular scanner placed along the spine. Device error is negligible with accuracy as high as 98%¹²¹ The device has been used in other yoga interventions.¹⁰³

Grip Strength will be measured using two trials for each hand with a hydraulic dynamometer. The best performance is selected for each side, and the average of the left and right hand is used for analysis. Painful or injured hands or wrists are not tested and the result of the good hand is used. Reliability has been shown to be high: $r=0.88-0.92$. Good predictive validity of grip strength has been shown for disability and mortality.¹²²

Core Stabilization and Strength. Prone and supine bridge positions will assess core stabilization.¹²³ Participants begin on their elbows in the prone position with shoulders, hips, and ankles aligned. The supine position is tested next, with knees flexed 90 degrees and pelvis raised from the floor with shoulders, hips, and knees aligned. Assessors record length of time (120 seconds max) that each position is held in proper form.

Heart rate. Physical exertion during yoga will be measured using Polar FT4 Heart Rate Monitors. Worn on the chest, they provide aggregate summary data such as maximum and mean heart rate during a workout.

Interventions:

There will be two interventions: Hatha Yoga and Restorative Yoga. Both interventions will meet 2 times a week for 12 weeks with at least one day of rest between each class. Individual classes will be 60 minutes long and led by a certified yoga instructor. Additionally, participants will be encouraged to practice yoga at home as guided in a home practice manual.

Hatha Yoga (HY)

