Statistical Management and Analysis: Qualitative data will be managed and analyzed by Co-I [name]. Results will be presented to the research team and additional sub-analyses will be conducted as needed before the intervention is modified. Health outcome data and mediational variables will be collected directly before and after the 12-week yoga program using physiological assessments and questionnaires. We will assess the effect size of the difference in change in health outcomes (pain interference, pain severity, and physical functioning) from pre- to post-intervention between

intervention groups using a linear random effects model. We will assess clustering by site with a likelihood ratio test. The point estimate of difference in change score between two groups and the 95% confidence interval for the estimated difference will be provided. We will also perform multivariate analysis and an adjusted effects size (with 95% CI) by including baseline characteristics that are significantly imbalanced between two groups as covariates in the random effects model. Analyses will be conducted by the biostatistician ([name]). The effect size estimates (and CI width) will help inform power calculations for the subsequent R01 submission. R software packages will be used for all statistical analyses.

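### Grip strength is scored on two hands or one depending on which can be tested that day, so a hand missed at only one visit puts a false change of either sign into the pre-post comparison

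*Combined protocol and SAP*

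**What the plan says.** The combined protocol and SAP define the measure in section 9, Physical Measures, Grip Strength: "Grip Strength will be measured using two trials for each hand with a hydraulic dynamometer". The normal score follows: "The best performance is selected for each side, and the average of the left and right hand is used for analysis". There is one exception: "Painful or injured hands or wrists are not tested and the result of the good hand is used".

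Section 9, Assessments and Randomization, sets two assessments, baseline and 12 weeks. Under Statistical Management and Analysis the plan adds: "Health outcome data and mediational variables will be collected directly before and after the 12-week yoga program using physiological assessments and questionnaires". The quantity to be estimated there is the between-group "difference in change in health outcomes (pain interference, pain severity, and physical functioning) from pre- to post-intervention".

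No section says that the same hand or hands must be scored at both visits, or how to score a participant whose hand was tested at one visit and not at the other.

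**The concern.** The exception is a rule for the day of testing. It gives a sensible value for a single visit but does not say what happens when two visits are compared. A participant with both hands tested at baseline and one hand at 12 weeks, or the reverse, has two scores that measure different things. Their difference mixes any real change in strength with the ordinary difference between that person's hands.

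The situation can arise. The eligibility criteria contain no hand or wrist exclusion, while a coexisting chronic pain problem is excluded. Hand pain among those enrolled is therefore more likely to be passing, and so present at one visit only. That is an inference; the documents give no frequency. What is at stake is the validity of any grip change reported for the affected participants and, through them, the arm means.

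**Working it through.** The documents state no power, precision or expected-change figure for grip, so there is nothing to reproduce. The check is algebra on the scoring rule.

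**Inputs from the documents**
- Both hands tested: mean of the best left and best right values (Grip Strength).
- One hand painful or injured: the other hand's value alone (Grip Strength).
- Two visits, baseline and 12 weeks (Assessments and Randomization).
- 50 randomised (section 9, Phase 2; section 10), taken as about 25 per arm. The synopsis says 60, which would be about 30 per arm.

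**Assumptions, not in the documents**
- Weaker hand 0%, 5%, 10% or 20% below the stronger; in absolute terms, a difference of 2 to 6 kg.
- Two affected participants in one arm, none in the other.
- SD of grip change 4 to 6 kg, used only to put the shift in proportion.

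**Per participant.** Let S be the stronger hand and W the weaker, with no true change between visits.

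| Hand untested | Visit missed | 12 weeks minus baseline | False change |
|---|---|---|---|
| Weaker | 12 weeks only | S − (S+W)/2 | +(S−W)/2 |
| Stronger | 12 weeks only | W − (S+W)/2 | −(S−W)/2 |
| Weaker | Baseline only | (S+W)/2 − S | −(S−W)/2 |
| Stronger | Baseline only | (S+W)/2 − W | +(S−W)/2 |

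The size is always (S−W)/2 and both signs occur. It is zero if the hands are equally strong; there is no such artefact if the same hand or hands are tested at both visits.

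Setting S = 100 and expressing the result relative to the two-hand mean:
- 0% asymmetry: 0.
- 5%: W = 95, mean 97.5, artefact 2.5; 2.5/97.5 = 2.6%.
- 10%: W = 90, mean 95, artefact 5; 5/95 = 5.3%.
- 20%: W = 80, mean 90, artefact 10; 10/90 = 11.1%.

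A difference of 2 to 6 kg gives an artefact of 2/2 = 1 kg to 6/2 = 3 kg.

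**Per arm.** The shift in an arm's mean change is the sum of the individual artefacts divided by the arm size. If two of 25 are affected with the same sign, it is 2/25 × 1 = 0.08 kg to 2/25 × 3 = 0.24 kg, in either direction. With 30 per arm the upper value is 2/30 × 3 = 0.20 kg. If the two artefacts have opposite signs and equal size, the shift is 0. In relative terms, at 10% asymmetry and all of one sign, 1, 2 or 5 affected of 25 give about 0.2%, 0.4% or 1.05% of mean grip; at 20% asymmetry, about 0.4%, 0.9% or 2.2%.

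**In proportion to precision.** The standard error of a between-arm difference in change is SD × √(2/25) = 0.283 × SD, or 1.13 to 1.70 kg for an SD of 4 to 6 kg. The same-sign shift is then 0.08/1.70 = 0.05 to 0.24/1.13 = 0.21 standard errors.

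**With both visits scored on the hands tested twice**, the false change is S − S = 0 or W − W = 0, whatever the asymmetry.

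**The case against.** The strongest reply is that this is an unstated detail for an uncommon case in a measure of little consequence. Pain interference is the primary outcome. The effect-size analysis names pain interference, pain severity and physical functioning, and section 9 measures physical function with two disability questionnaires, not grip. The study is a feasibility pilot that disclaims any conclusion on efficacy. A best value is selected for each side, so a same-hand change could be worked out later if those values are kept. The arm-level shift is a small fraction of a standard error even when all artefacts share a sign.

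Most of this stands, and it limits the point to a minor one. It does not remove it. The Grip Strength text says that "the average of the left and right hand is used for analysis", and the physiological measures are taken before and after the programme, so a pre-post comparison of grip is the natural use, although the plan does not spell one out. The rule as written gives a wrong change for an affected participant. Nor does the plan say that side-specific values are retained; if only the final score is recorded, the artefact cannot be undone.

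A reader might go further and infer that the artefact favours improvement, because an injured hand is dropped and the better one kept, and that it would flatter the more active yoga arm. The documents do not support either step. The rule drops the painful hand, not the hand that was weaker beforehand. If the stronger hand is hurt during the study, the result is a false fall. No section reports hand or wrist injuries by type of yoga, and the hatha programme is described as using modifications and props to limit injury.

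**Conclusion.** The point holds in a limited form. When a hand is tested at only one of the two visits, the grip change compares unlike quantities and carries an error of half the between-hand difference. That algebra needs no assumption beyond the rule as written and its application at each visit; it is 1 to 3 kg per affected participant if the hands differ by an assumed 2 to 6 kg.

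The effect on an arm mean is probably small. The 0.08 to 0.24 kg figure assumes two affected participants of 25 in one arm and the same sign for both, and the documents supply none of these. Without a frequency, a between-hand difference or a link between injury and hand dominance, no direction can be claimed for either arm. The trial's feasibility aims and its primary outcome are untouched. This is an inexpensive improvement, best made before data collection.

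**What to change.** Add a sentence to the Grip Strength paragraph: each hand's best value, and whether the hand was tested, will be recorded at each visit, and any grip change will use only the hand or hands tested at both visits (the two-hand mean if both were tested twice, otherwise the same single hand at both). If grip is analysed in the random effects model, the baseline and 12-week scores should be built from the same hands. If no hand was tested at both visits, the change should be treated as missing. The number of participants scored on one hand should be reported by arm.

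The cost is that sentence and two side-specific fields per visit on the form. No new measurement is needed. A single-hand change says nothing about the untested hand, but the present rule does not measure that hand either.

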Aim 3: Modify an existing yoga intervention for the preferences of active-duty military and to address both CLBP and CNP. Based on the results of the qualitative interviews, the existing yoga intervention designed for VA patients with CLBP will be refined and adjusted to better fit the preferences of active-duty military personnel with CLBP or CNP. This process will start with the investigators and yoga experts reviewing [name] report of the qualitative results. The team will also independently review a current Yoga for CLBP manual being used by [name], the Cramer et al. manuscript which lists the 14 yoga poses they selected for treating CNP, and other yoga texts. Investigators and experts will then convene at UCSD for an extended afternoon meeting to select of a pool of possible poses. The PI will then work with orthopedic surgeon [name] and yoga expert [name] to propose specific changes to the intervention. The revisions will be presented to the other collaborators for review and additional discussion. Possible examples include a slightly faster pace, adding postures for additional challenge for those with less impairment (yet easily modified to be safe for all), additional attention tasks or imagery, and further trauma sensitivity. All changes and the rationale behind them will be documented.

Phase 2

Please note: before we begin Phase 2 we will also need to obtain IRB approval from NMCS D for activities that will take place at that site. Once we obtain IRB approval from NMCS D, we will provide a copy to UCSD's IRB prior to commencing any activities at that site. In Phase 2 we will accomplish Aims 4-6 by conducting a pilot RCT with 2 yoga interventions. We will recruit 25 people at each of two sites, one in a military medical facility (NMCS D) and one in a community yoga studio (Yoga Oceanside) near a large military base for a total of 50 participants. Once 25 people have been recruited at each site, they will be randomized to attend either active hatha yoga or restorative yoga.

Screening and Inclusion/Exclusion Criteria.

50 active-duty military personnel with CLBP will be recruited and randomized to either active hatha yoga or to restorative yoga. Inclusion criteria are as follows:

Inclusion:

- Diagnosis of CLBP or CNP > 6 months
- Willing to attend a yoga program for 12 weeks
- Willing to complete 3 assessments
- English literacy
- Have had no changes in pain treatments in the past month

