The HY intervention will be led by a certified instructor at each site. Both instructors will be trained by [name] who has been practicing yoga for over 16 years and has over 8 years of teaching experience and is the main instructor for [name] for Vets with CLBP. (NOTE: We will model the HY intervention after the current Yoga for CLBP intervention which is a classical hatha yoga with influences from Viniyoga and Iyengar yoga. Both Viniyoga and Iyengar yoga styles emphasize modifications and adaptations including the use of props such as straps and blocks in order to minimize the risk of injury and make the poses accessible to people with health problems and limitations.) The certified yoga instructors will lead participants through a series of 23 yoga poses (32 total variations) at a slow-moderate pace. Instructors will be asked to follow the manual which will help standardize the yoga intervention. The manual contains pictures and a description of how to perform each pose with typical instructor dialogue. The dialogue may be paraphrased and varied slightly, yet promotes more consistent replication and generalization of results. The manual includes some poses that could aggravate back conditions if they are not modified for some people. That is why multiple modifications are shown and many of the poses shown are only worked up to after weeks of practice and individual attention from the instructor. The more challenging poses are not included in the home practice manuals. The importance of attending all sessions will be stressed during session 1 and throughout all sessions. Participants who miss a session without notifying the instructor will be contacted to check on the reason for non-attendance. Participants will also receive a home practice manual containing some basic, safe postures that can be performed in 10-15 minutes on days they will not be attending the formal in-person sessions. Participants will be encouraged to not push themselves as much when practicing at home and to stop when pain or discomfort becomes noticeable. They will be encouraged to consult with the instructor individually before and after

class about any problems or difficulties they are encountering at home or in the formal sessions.

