The details of the RY intervention will be developed using the expertise of our team of experienced yoga instructors and the feedback from the Phase 1 Qualitative Interviews. Our yoga experts have training and experience delivering RY sessions. The team will read and discuss *The iRest Program for Healing PTSD*,¹⁰¹ a recent book that outlines the iRest approach to treating PTSD. The team will also review and discuss a RY practice manual developed for metabolic syndrome by our colleagues at UCSD and UCSF. The 42-page manual explains 5 different poses with an additional 8 modifications to those poses, and provides pictures and helpful tips. Based on these materials, our yoga experts will develop our RY intervention and create an intervention manual and a home practice manual. The intervention will occur 2x weekly for 12 weeks – each class will be 60 minutes to match that timeframe of the active yoga intervention.

Treatment Fidelity.

Instructor fidelity to the yoga intervention manual will be evaluated using video recordings of yoga intervention sessions. All yoga sessions will be recorded with a digital camcorder and tripod placed in the back of the yoga room. Instructors and participants will be aware of and consent to the recordings. We do not plan to analyze all recorded sessions, but recording all sessions will standardize the presence of the camera across all sessions and result in more rapid habituation. Of the 24 sessions videotaped at each site, we will randomly select a session from weeks 1-4, weeks 5-8, and weeks 9-12 for review by a yoga instructor from Yoga Oceanside. They will review the sessions using a manual checklist for instructor adherence to the yoga manuals, which will consist of a Yes/No, blank, and 0-10 rating scale for each procedure or instruction.

Data management. Questionnaires will be formatted by the project coordinator under the supervision of [name] (PI). Formatting will be designed to reduce recording errors and facilitate computer scanning and verification. Forms will be de-identified to protect confidentiality, and data will be scanned and verified by the data manager (and project coordinator). The project coordinator will monitor the quality of the questionnaire data as soon as they are collected to achieve prompt resolution of errors and omissions. Data will be stored on a password protected secure network server at UCSD. Access privileges are limited to essential staff.

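### Clustering is checked only between two sites, although both arms are taught in classes; if classmates' outcomes are correlated, the reported 95% CI is too narrow

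*Combined protocol and SAP*

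**What the plan says.** Participants are randomised individually within site. Section 9 (Phase 2) states: "We will recruit 25 people at each of two sites". Section 9 (Assessments and Randomization) adds: "There will be one block file for each site, with 30 digits in each file, allowing each site to have a balanced randomization".

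Delivery is in groups. Section 9 (Interventions) says "Both interventions will meet 2 times a week for 12 weeks" and "Individual classes will be 60 minutes long and led by a certified yoga instructor". For the Hatha arm, "The HY intervention will be led by a certified instructor at each site"; for the Restorative arm the number of instructors and who they are is not specified.

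The number of classes is not stated. Section 9 (Treatment Fidelity) says every session will be recorded and then refers to a count: "Of the 24 sessions videotaped at each site". Two sessions a week for 12 weeks is 24 per arm, so two separate arms would give 48 per site.

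Section 9 (Statistical Management and Analysis) specifies a linear random effects model without listing its random effects, a 95% CI for the difference in change, and one clustering check: "We will assess clustering by site with a likelihood ratio test". On how the results will be used it says: "The effect size estimates (and CI width) will help inform power calculations for the subsequent R01 submission".

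**The concern.** The plan treats clustering as relevant but looks for it at the wrong level. A site effect is shared by both arms at that site, so it largely drops out of the arm difference. A class effect belongs to one arm only. Classmates share an instructor, a room, a schedule and each other's company for 24 sessions, and whatever they share stays in the arm difference. An interval built on independent individuals leaves that variance out.

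No efficacy decision depends on this interval, because Section 17 says the study is not powered for efficacy. What is at stake is Aim 6 (Section 6): the pilot exists partly to supply inputs for the next trial, and CI width is one of the inputs it names. An interval that is too narrow overstates how well the arm difference has been measured.

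**Working it through.** The plan gives no SD, ICC, power or CI width, so there is no figure of its own to reproduce.

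**Inputs from the documents.** 2 sites × 25 = 50 participants; balanced allocation within site, taken as 1:1; 95% confidence.

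**Assumptions.** Complete follow-up; class ICC ρ of 0.01, 0.02, 0.05 or 0.10; and either (a) four classes, one per arm per site, with mean size m = 50/4 = 12.5, or (b) eight classes, with m = 50/8 = 6.25.

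**Step 1: why site cancels and class does not.** The arm difference is the average over sites of (Hatha mean − Restorative mean). A site effect enters both means at its site and subtracts out. A class effect enters only one of them.

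**Step 2: variance.** With total variance σ², a class mean has variance σ²[1 + (m − 1)ρ]/m. Averaged over the classes in each arm:

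Var(difference) = (4σ²/N) × [1 + (m − 1)ρ]

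The SE multiplier is therefore √[1 + (m − 1)ρ]. For four classes and ρ = 0.05 this is √(1 + 11.5 × 0.05) = √1.575 = 1.25.

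**Step 3: half-width and coverage.** Ignoring class, the half-width is t(47) × √(4/50) = 0.57 SD. Multiply by the factor above to allow for class. Analytic coverage of the uncorrected interval is 2Φ(1.96/multiplier) − 1. Simulated coverage is from 40,000 trials analysed by least squares with arm and site and a t-based CI.

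| Class ICC | Classes | SE multiplier | Half-width needed (SD) | Coverage, analytic | Coverage, simulated |
|---|---|---|---|---|---|
| 0.01 | 4 | 1.06 | 0.60 | 93.7% | 93.9% |
| 0.02 | 4 | 1.11 | 0.63 | 92.3% | 92.1% |
| 0.05 | 4 | 1.25 | 0.71 | 88.2% | 87.7% |
| 0.10 | 4 | 1.47 | 0.83 | 81.9% | 80.8% |
| 0.01 | 8 | 1.03 | 0.58 | 94.4% | 94.3% |
| 0.02 | 8 | 1.05 | 0.60 | 93.8% | 93.6% |
| 0.05 | 8 | 1.12 | 0.64 | 91.9% | 91.8% |
| 0.10 | 8 | 1.23 | 0.70 | 88.8% | 88.4% |

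At ICC 0 the simulation gives 94.9% (four classes) and 95.2% (eight). Effective N with four classes is 50/1.575 = 31.7 at ICC 0.05 and 50/2.15 = 23.3 at 0.10.

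**Step 4: does a site term or the site test help?** No. With four classes, a random site intercept kept or dropped by the likelihood ratio test gives coverage of 93.7%, 92.0%, 88.0% and 80.6% across the same ICCs. That test rejects in only 1.2% to 7.8% of those trials (no true site effect), so it would rarely draw attention to the problem. Its power against a true site effect is also low: by maximum likelihood, about 5–7% at site ICC 0.05 and 12–16% at 0.10. That weakness does no harm to the CI by itself. With a site effect only and no site term, coverage is 95.1% and 95.3% at those two site ICCs.

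**Step 5: instructors.** If one person teaches both arms at a site, the instructor effect cancels and coverage stays at 95%. With a different instructor for each arm at each site, coverage falls to 93.8%, 92.2%, 87.9% and 80.9% at instructor ICC 0.01, 0.02, 0.05 and 0.10, even with eight classes.

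**Step 6: sample size.** Section 5 gives 60 participants, and the two files of 30 digits also total 60. With N = 60 and four classes of 15, the multipliers are 1.07, 1.13, 1.30 and 1.55.

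**The case against.** The case for leaving this alone has five parts.

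- **Little of what matters for planning is affected.** The point estimate is unbiased, and the residual SD is only about 2–4% low at ICC 0.05–0.10 with four classes. These are the usual sample-size inputs. This stands, and it limits the finding to the CI width. The plan does, however, name that width as an input.
- **The size is assumed.** The documents give neither ICC nor class count. Coverage of 81% needs an ICC of 0.10 together with four classes, or separate instructors per arm and site. At ICC 0.01–0.02 the change is small. This also stands; only the direction is certain once the ICC exceeds zero.
- **Instructor variation is limited by design.** The Hatha instructors share a trainer and follow a manual, a Restorative manual is planned, and sampled sessions are checked for adherence. This argues for the lower part of the ICC range for instructors. It does not remove what classmates share.
- **The unlisted random effects might include class.** This cannot be ruled out. It is a reason to list them.
- **A fixed site effect cures no undercoverage.** True. It is recommended because randomisation is by site and because it removes a test with little power and no stated consequence.

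The trial also cannot estimate the ICC, so inflated intervals add no data. They show how far the stated precision depends on assuming independence within class.

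**Conclusion.** The concern holds. As written, the plan checks clustering at a level that largely cancels from the arm contrast, and it states no term for the level that does not. If the class ICC is above zero, the 95% CI is too narrow. At N = 50 and ICC 0.01–0.10, the required half-width is 0.60–0.83 SD with four classes or 0.58–0.70 SD with eight, against 0.57 SD when class is ignored.

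These figures rest on assumed ICCs and class counts, 1:1 allocation and complete follow-up. Losses to follow-up, or participants mixing across class times, would reduce the effect; N = 60 in the same number of classes would increase it. The consequence is an over-precise planning input for the R01. It is not a biased estimate or a false efficacy claim. The change should be made, but it does not threaten the pilot's feasibility aims.

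**What to change.** - Fit site as a fixed effect in every outcome model in place of the likelihood ratio test, and list the random effects in the model.
- State the number of class series and instructors per arm and site, and reconcile this with the 24 videotaped sessions per site.
- Carry each participant's class and instructor into the analysis data set. The sign-in logs described in Section 9 (Attendance/Home practice) can supply class.
- State that so few classes cannot estimate the class variance. A class-level analysis with four classes has 4 − 2 = 2 degrees of freedom. It restores coverage, but its average half-width is about 1.14 SD at ICC 0.01 and 1.58 SD at 0.10, which is too wide to be useful.
- Beside the individual-level CI, report as a sensitivity analysis intervals with the SE multiplied by √[1 + (m − 1) × ICC] at ICC 0.01, 0.02, 0.05 and 0.10. Take m as the actual mean class size, or the number of participants per instructor within an arm if that is larger. In simulation with the correct ICC, this gives coverage of 94.2–95.0% with four classes and 94.5–95.1% with eight.
- Carry that range into the R01 sample size.

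The cost is SAP wording, two variables and a few lines of R. The drawback is that the wider intervals rest on an ICC that this trial cannot estimate.
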